3 OBJECTIVE

Primary Objective: to compare a Heart-Team *clinical decision making strategy* either based solely on non-invasive CT angiography (GE RevolutionTM) with and without adjunctive HeartFlow FFR_{CT} or based solely on conventional invasive angiography.

Secondary objectives:

To evaluate in a population with multivessel disease, the outcomes *between* two strategies (noninvasive '*CT first algorithm*' and invasive conventional '*Angiography first algorithm*') and *within* these two strategies (based on differences in availability of sources of information). The sources of information are:

- Invasive Angiography
- Non-invasive GE Revolution CT
- Functional anatomy by non-invasive FFR_{CT} (Heartflow)

The results of information are:

- Agreement on treatment recommendation
- Agreement on treatment recommendation between different levels of available information
- Agreement in coronary stenosis segments to be revascularized
- Anatomical SYNTAX Score and the resulting SYNTAX Score II

4 STUDY DESIGN

The SYNTAX III REVOLUTION Trial is a multicenter, all-comers* trial aiming at randomizing two Heart Teams who would have to make a decision between surgical or percutaneous treatment according to either an invasive conventional angiography or a non-invasive multislice CT angiography assessment in approximately 223 patients in approximately 5-10 interventional cardiology centers in Europe. *Patients with de novo 3-vessel disease or left-main disease (isolated or associated with 1, 2 or 3 vessel disease) will be eligible.

For each given patient the Heart Team is randomly assigned to an "Angio-First" or a "CT-First" decision algorithm. There will be two (2) independent Heart Teams per hospital, and each patient will be assessed by both teams. The concordance or discordance of decision makings based on

Protocol ECRI-004 Version 1.0 Page 24 of 66

either conventional angiography (Angio first algorithm) or MSCT angiography (CT first algorithm) will be assessed and constitute the primary endpoint of the trial. In addition, the incremental value of FFR_{CT} in the decision making of the Heart Team arm allocated primarily to the assessment of the MSCT (CT first algorithm) will be a secondary endpoint.

Patient study participation will end after final Heart Team treatment decision. The ultimate choice of treatment is up to the discretion of the physician/Heart Team.

5 ENDPOINTS

5.1 Primary Endpoint

Inter-rater agreement, as assessed by Cohen's Kappa, on revascularization strategy of two Heart Teams using an "Angio-first" algorithm (based on invasive SYNTAX Score II) or a "CT-first" algorithm (based on non-invasive SYNTAX Score II, without FFR_{CT}).

The Heart Team consensus on therapeutic strategy is made according to the following 3 options:

CABG-only.

1. *CABG-only*. Patient should be treated by CABG due to high 4-year mortality of PCI according to therapeutic recommendation of SYNTAX Score II.

PCI-only/ Equipoise.

1. *Equipoise*. Patient could be treated by either CABG or PCI, considering that the 4-year mortality prediction is similar between PCI and CABG.

2. *PCI-only*. Patient should be treated by PCI due to high 4-year mortality of CABG according to therapeutic recommendation of SYNTAX Score II

*The Heart Team can overrule the SYNTAX Score II therapeutic recommendation whenever the Heart Team identifies significant additional clinical risks which are not addressed in the SYNTAX Score II.

5.2 Secondary endpoints

Secondary endpoints of this study are to assess:

- Level of agreement in the decision making strategy based on CT only without functional assessment and the decision making strategy based on CT with functional assessment ("CT first" algorithm group).
- Level of agreement in the decision making strategy based on CT only (with functional assessment) and the decision making strategy based on CT with functional assessment and conventional angiography ("CT first" algorithm group).

- Level of agreement in the decision making strategy based on conventional angiography only and the decision making strategy based on CT with functional assessment and conventional angiography ("Angio first" algorithm group).
- Inter-rater agreement on revascularization strategy (based on conventional angiography and CT with functional assessment) of two Heart Teams using an "Angio-first" algorithm or a "CT-first" algorithm.
- Anatomical SYNTAX Score calculation based on non-invasive GE Revolution CT (visual by Heart Team involving a radiologist) and the resulting SYNTAX Score II.
- Anatomical SYNTAX Score calculation based on non-invasive GE Revolution CT (visual by Core Lab) and the resulting SYNTAX Score II.
- Anatomical SYNTAX Score calculation based invasive Angiography (visual by Heart Team) and the resulting SYNTAX Score II.
- Anatomical SYNTAX Score calculation based on invasive Angiography (visual by Core Lab) and the resulting SYNTAX Score II.
- CT based functional SYNTAX Score (FFR_{CT} as assessed by Heartflow)
- Concordance in SYNTAX Score(s) between and within strategies
- Agreement in coronary stenosis segments to be revascularized between and within strategies.

6 SUBJECT SELECTION

i). Patients with left main (isolated, or associated with 1, 2 or 3 vessel disease) or de novo 3-vessel coronary artery disease (DS \geq 50%) who are able to undergo cardiac CT with a GE high-definition RevolutionTM multi-slice CT scanner.

ii). Patients can be enrolled from a referral site, externally diagnosed and referred to the cardiologist and/or surgeon; or patients can be diagnosed internally. If the patient is diagnosed internally, the physician who performed the diagnosis should not be involved in the Heart-Team(s).

iii). The enrolment criteria will be unrestrictive all anatomical SYNTAX Scores are eligible for initial screening similar to the SYNTAX I and II studies. As per the original SYNTAX Trial, prior CABG or PCI will be one of the few exclusion criteria.

6.1 Inclusion Criteria

- Patients with at least 1 stenosis (angiographic, visually determined de novo lesions with ≥50% DS) in all 3 major epicardial territories (LAD and/or side branch, CX and/or side branch, RCA and/or side branch) supplying viable myocardium with or without left main involvement;
- 2. Patients with hypoplastic RCA with absence of descending posterior and presence of a lesion in the LAD and CX territories may be included in the trial as a 3VD equivalent;
- Vessel size should be at least 1.5 mm in diameter as visually assessed in diagnostic angiogram;
- 4. Patients with chronic stable angina or stabilized acute coronary syndrome (inclusion criteria of the SYNTAX I study):
 - a) stable (Canadian Cardiovascular Society Class 1, 2, 3 or 4) angina pectoris;

b) or unstable (Braunwald class IB, IC, IIB, IIC, IIIB, IIIC) angina pectoris and ischemia with normal cardiac enzyme values prior to enrollment;

c) or patients with atypical chest pain or those who are asymptomatic provided they have myocardial ischemia (e.g. treadmill exercise test, radionuclide scintigraphy, stress echocardiography);

- 5. All anatomical SYNTAX Scores are eligible;
- 6. Patient amenable to a MSCT coronary angiography (e.g. no claustrophobia, high heartrate not amenable to beta-blockers, poor renal function, etc., up to discretion of investigator);
- 7. Patient has been informed of the nature of the study and agrees to its provisions and has provided written informed consent as approved by the Ethical Committee of the respective clinical site;

6.2 Exclusion Criteria

Candidates will be ineligible for enrolment in the study if any of the following conditions apply:

- 1. Under the age of 18 years;
- 2. Unable to give Informed Consent;
- Known pregnancy at time of enrolment. Female of childbearing potential (and last menstruation within the last 12 months), who are not taking adequate contraceptives. Female who is breastfeeding at time of enrolment;
- 4. Prior PCI or CABG; history of coronary stent implantation;
- 5. Evidence of evolving or ongoing acute myocardial infarction (AMI) in ECG and/or elevated cardiac biomarkers (according to local standard hospital practice) have not returned within normal limits at the time of enrollment;
- Concomitant cardiac valve disease requiring surgical therapy (reconstruction or replacement);
- 7. Single or two-vessel disease (at time of Heart Team consensus);
- 8. Atrial fibrillation or significant arrhythmias;
- 9. Known allergy to iodinated contrast;
- 10. A Body Mass Index (BMI) of 35 or greater;
- 11. Participation in another trial with an investigational drug or device.

7 STUDY PROCEDURES

7.1 Screening

To assess the eligibility of the patient according to the inclusion/exclusion criteria, the presence of left main disease (isolated, or associated with 1, 2 or 3 vessel disease) or de novo 3-vessel coronary artery disease must be diagnosed on conventional angiography and/ or MSCT before randomization.

7.2 Patient Information and Informed Consent

If the eligibility of the patient is confirmed according to inclusion and exclusion criteria, patients must be consented prior to undergoing any study-specific procedures. Once the patient's general eligibility for the study is met, the background of the proposed study and the benefits and risks of the study must be explained to the patient prior to obtaining informed consent. Only those patients who sign the Ethics Committee approved informed consent form prior to any study-specific procedures (MSCT scanning with GE 256-slice REVOLUTION scanner) are candidates for actual enrolment in the study. Failure to provide written informed consent renders the patient ineligible for the study.

The investigator and/or designee must also clearly document the process of obtaining informed consent in the subject's source documents. The voluntary process of obtaining informed consent confirms the subject's willingness to participate in the study. It is the investigator's responsibility to ensure that the informed consent process is performed in accordance with ISO14155, EC requirements and country specific regulations.

7.3 Baseline evaluation prior to MSCT/ Heart Team discussion

As part of good clinical practice, the following routine laboratory tests must be performed prior to MSCT scanning/Heart Team randomization:

- creatinine clearance (Cockcroft-Gault⁷¹);

According to good routine local clinical practice, left ventricular ejection fraction (percentage) should be assessed quantitatively by either echo-cardiography, or conventional left ventriculography or other modalities. In addition, the history of chronic obstructive pulmonary disease, peripheral artery disease should be evaluated according to the EuroScore (I) definition.

7.4 MSCT

Prior to the Heart Team randomization, a MSCT scan must be obtained utilizing the 256-slice GE Revolution* CT scanner. Refer to Appendix IV for MSCT acquisition guidelines.

*A patient may be diagnosed/enrolled based on previously performed MSCT (but solely, if that CT was performed with the 256-slice GE Revolution CT scanner and within 1 month prior to patient enrolment.

 FFR_{CT} will be used in the incremental process of Heart Team discussion (= secondary endpoint). The MSCT-derived FFR (FFR_{CT}) will only be disclosed after the first decision making has been concluded.

7.5 Anatomical SYNTAX Score, SYNTAX Score II and functional anatomy (FFR_{CT})

The baseline anatomical SYNTAX Score for angiography and for MSCT and SYNTAX Score II should be calculated prior to the start of the Heart Team meeting(s) and must be recorded in the eCRF.

The diagnostic angiograms and acquired and reconstructed MSCT images should be transferred automatically using AG Mednet to the independent Core Lab (Cardialysis, B.V., Rotterdam, NL) and to HeartFlow Inc. (Redwood city, California, USA) for the functional assessment derived from MSCT (FFR_{CT}).

Additionally, anatomical SYNTAX Score (angiography and CT) will be performed by the Core Laboratory. The site/Heart Team may consult the Core Lab SYNTAX Score (I and II) during the Heart Team meeting/treatment decision-making process.

The site/Heart Team may consult the Core Lab SYNTAX Score (I and II) during the Heart Team meeting/treatment decision-making process.

The site/Heart Team will also receive the functional anatomy (FFR_{CT}) for consultation.

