7.7 Heart Team meeting structure & organization

The Heart Team should involve an interventional cardiologist, cardiac surgeon, radiologist (experienced coronary CT reader) and study coordinator.

It is recommended to execute the different levels of decision making during *one* Heart Team session. In other words, one should start the Heart Team meeting only when all information is available and accessible, i.e. anatomic SYNTAX Score by Angio and CT (by site and by Core Lab), SYNTAX Score II and functional anatomy (FFR_{CT}). Randomization is performed via the eCRF module. The *Heart Teams* are randomized to one of two groups (1:1) to either 'Angio-first algorithm' or 'MSCT-first' algorithm.

Angio first algorithm: Screen the patients first by means of conventional invasive angiography (i.e. anatomical SYNTAX Score [visual] and SYNTAX Score II) and record the first decision making on choice of revascularization (PCI or CABG), planning of revascularization measures (# of stents / # of grafts), and localization of diseased segments needing revascularization in the

eCRF. As an external reference, the independent Core Lab also provides anatomical SYNTAX Score for consultation. After the first decision making recording, the additional information of CT and the functional severity assessment is disclosed and the Heart Team completes the second decision based on information derived from both modalities.

CT first algorithm: Screen the patients first by means of non-invasive CT (i.e. anatomic SYNTAX Score [visual by experienced coronary CT reader/radiologist] and SYNTAX Score II and record the first decision making on choice of revascularization (PCI or CABG), planning of revascularization measures (# of stents / # of grafts), and localization of diseased segments needing revascularization in the eCRF. The radiologist of the Heart Team provides anatomical SYNTAX Score on MSCT, which is primarily used for decision making. As an external reference, the independent Core Lab also provides anatomical SYNTAX Score on MSCT for consultation.

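### Does the unqualified permission to consult Core Lab SYNTAX Scores let a Heart Team see the other modality before its first decision?

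*Combined protocol and SAP*

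**What the plan says.** Section 7.5 has the site calculate the anatomical scores and SYNTAX Score II in advance: they "should be calculated prior to the start of the Heart Team meeting(s) and must be recorded in the eCRF". It continues: "Additionally, anatomical SYNTAX Score (angiography and CT) will be performed by the Core Laboratory". It then states, printed twice, that "The site/Heart Team may consult the Core Lab SYNTAX Score (I and II) during the Heart Team meeting/treatment decision-making process". The section closes by saying that the team also receives FFR_CT, again without naming a stage.

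The order of events is set elsewhere:

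- Section 7.4: FFR_CT "will only be disclosed after the first decision making has been concluded".
- Section 7.7, Angio-first: "As an external reference, the independent Core Lab also provides anatomical SYNTAX Score for consultation". The next sentence reads: "After the first decision making recording, the additional information of CT and the functional severity assessment is disclosed".
- Section 7.7, CT-first: the radiologist's CT score is the one "which is primarily used for decision making", and "As an external reference, the independent Core Lab also provides anatomical SYNTAX Score on MSCT for consultation". FFR_CT follows after the first decision, and angiography after the second.
- Section 7.7, closing note: the team co-signs each decision in the eCRF, with date and time, before it is unblinded to the complementary imaging or functional information.
- Section 7.8: access to Core Lab scores is described in a separate manual, which is not among the documents reviewed.

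**The concern.** The primary kappa compares one decision made from angiography with one made from CT without FFR_CT. It is the trial's only formal test, and its meaning depends on each team seeing one modality at its first decision. Section 7.5 read alone does not protect that. The Core Lab holds both scores, the permission covers the whole decision process, and the Angio-first sentence in section 7.7 does not name the modality of the Core Lab score, whereas the CT-first sentence does. Section 7.7 also recommends starting the meeting only when every score, from site and Core Lab and for both modalities, is at hand. If a team saw the other modality's score early, the two decisions could converge for reasons unrelated to how well CT stands in for angiography.

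A second worry is traceability. The items that section 7.7 lists for each decision are treatment mode, numbers of vessels or lesions, and segments. Nothing shows whether the Core Lab score was consulted. Nor do the documents say whether the Core Lab's two reads are blinded to each other.

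**Working it through.** **1. The plan's own figure.** Inputs from section 8.3: kappa 0.80 against 0.60, 30% CABG-only under both algorithms, two-sided 5%, 90% power, 10% attrition. With margin p = 0.30, the chance that both teams choose CABG-only is 0.09 + 0.21k, that they differ 0.42(1 − k), and that neither does 0.49 + 0.21k.

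- At k = 0.60: 0.216, 0.168, 0.616. At k = 0.80: 0.258, 0.084, 0.658.
- Goodness-of-fit sample size: (1.960 + 1.282)² / [0.042²/0.216 + 0.084²/0.168 + 0.042²/0.616] = 10.51 / 0.05303 = 198.1, so 199.
- Large-sample variance at k = 0.60 (0.768 per patient): 10.51 × 0.768 / 0.2² = 201.7, so 202.
- Attrition: 200 / 0.90 = 222.2, so 223.

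The stated 200 and 223 are reproduced. Nothing in this point alters them.

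**2. Is cross-modality access permitted before the first decision?** Set the sections side by side.

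- In the Angio-first text, the Core Lab sentence comes directly before the sentence that releases CT information once the first decision is recorded. If the Core Lab score offered at that stage included CT, the next sentence would have nothing left to withhold. The score meant there is the angiographic one.
- In the CT-first text the modality is named as MSCT, and angiography comes only before the third decision.
- The co-signature rule covers all complementary information. It does not name the Core Lab score, but a Core Lab reading of the CT is CT information.
- Sections 5.1 and 8.5 define the compared decisions as based on the invasive score and on the non-invasive score without FFR_CT. A first decision informed by the other modality would not be the endpoint as defined.
- The open FFR_CT sentence in section 7.5 is governed in the same way by section 7.4.

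Section 7.5 says what may be consulted; section 7.7 says when. Read together they leave loose drafting and no conflict in conduct.

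**3. What would be at stake if the literal reading governed.** Assume, with no figure in the documents, that a shared score forces agreement in a share f of patients. Kappa becomes (1 − f)k + f. From k = 0.60, f = 0.10, 0.20 and 0.30 give 0.64, 0.68 and 0.72. Simulation of the section 8.5 rule at n = 200 gives a positive trial in about 12%, 32% and 59%, against 3.6% with no leak (exact enumeration). That would matter, but it requires the disclosure that step 2 shows to be barred.

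**4. What remains permitted: own-modality consultation.** Let each team independently follow the Core Lab score of its own modality in a share u of patients. Let kCL be the agreement of the Core Lab's two answers, and leave agreement at k when only one team follows. Then kappa = (1 − u²)k + u²·kCL. Neither u nor kCL is in the documents. Exact enumeration at n = 200 gives:

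- k = 0.60, u = 50%: kCL = 0.50 gives 0.75 × 0.60 + 0.25 × 0.50 = 0.575, positive in 1.5%; kCL = 0.90 gives 0.675, positive in 29%.
- k = 0.60, u = 25%: kappa 0.594 to 0.619 over the same range, positive in 2.9% to 6.7%.
- k = 0.80, u = 50%: kappa 0.725 to 0.825, positive in 63% to 99%, against 97% without consultation.

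The direction is unknown and the size depends wholly on the assumed use. Tying section 7.5 to the allocated modality would leave all these numbers as they are, because own-modality consultation would continue.

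**The case for a change.** The strongest reply is that a protocol should not need to be read across sections to protect its primary endpoint, least of all when all the scores are recommended to be at hand when the meeting starts. Where the permission is broad and the Angio-first sentence silent, a site could read it the wrong way, and nobody would know because consultation is not a listed item.

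Part of this stands. The sentence in section 7.5 is unqualified, the Angio-first text omits a word that the CT-first text has, and consultation is not among the listed items. Three things limit what follows.

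- The practical access rule belongs to the manual named in section 7.8, so the documents cannot show that it is missing.
- The list in section 7.7 sets out the content of a decision; it is not an eCRF specification, and section 13.6 describes eCRF content only by example. Some indirect checking is already possible from the site scores recorded before the meeting, the Core Lab scores (section 5.2), the timed co-signatures and the recorded reasons for overruling the calculator.
- The extra analyses one might ask for add little. Kappa in patients without any consultation rests on a self-selected subset. With a per-patient variance of 0.433 at kappa 0.80, its 95% interval would be about 0.62 to 0.98 with 50 patients and 0.67 to 0.93 with 100. Kappa between the calculator's recommendations from site scores would describe the calculator, not the Heart Team.

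Silence on mutual blinding of the Core Lab reads is not evidence that they are unblinded.

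**Conclusion.** No change to the plan is needed. The other modality's Core Lab score is complementary information under section 7.7 and is withheld until the first decision is co-signed. A team that follows the protocol as a whole produces the kappa defined in sections 5.1 and 8.5. Consulting the Core Lab score of one's own modality is part of both declared algorithms, so any effect on kappa belongs to the strategies being compared and is not a bias in the analysis. It also leaves intact the blinding to the other team's decision required by section 7.6.

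The effect on sample size, primary analysis and decision rule is nil. The illustrated shifts (1.5% to 29% at agreement 0.60, and 63% to 99% at 0.80, with half of each team's decisions following the Core Lab) rest on assumed rates and describe permitted conduct.

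The conclusion assumes that sites treat section 7.7 as the operative sequence and that the section 7.8 manual does not contradict it. Naming angiography in the Angio-first sentence and noting whether the Core Lab score was consulted would be tidy, but would only write down the existing intent.

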7.6 Randomization

Before the start of enrolment, two Heart Teams (A and B) are formed and registered at each site, including at least one physician from each sub-speciality (i.e., radiologist, cardiac surgeon and interventional cardiologist). When a patient is enrolled, the algorithm of decision making is randomly allocated to two Heart Teams (i.e. Heart Team A: CT first, Heart Team B: Angiography first, or Heart Team A: Angiography first, Heart Team B: CT first) in order to ensure that the two Heart Teams experience both decision-making processes equally (e.g. CT based or Angio based). According to the allocated sequence, two Heart Teams discuss and make a treatment decision independently (blinded to the decision made by the other Heart Team).

In case any member of the Heart Team is not available due to logistical (e.g. on-call, congress, holiday) or other reasons (e.g. pre-exposure to angiography or MSCT) the site is allowed to have 'back-up physicians' for Heart Team A and Heart Team B. In other words, in order to prevent any delay in clinical decision making, the Heart Team can still proceed with the discussion as long as at least one physician from all three specialities is available.

